## **NUMBER OF PARTICIPANTS**

The study will enroll *up to* 65 participants to assess the safety and tolerability of repeated dosing of RO7049665 (approximately 10 participants, randomized in the ratio of 4:1 RO7049665 to placebo, per cohort).

## **CONCOMITANT MEDICATIONS**

### **Permitted Therapy**

All concomitant medications throughout the duration of the study should be recorded in the case report form. Use of the following therapies will be permitted, as specified below:

- Paracetamol is allowed up to a maximum dose of 2 g/day up to 48 hours prior to each RO7049665 or placebo dosing, not to exceed 4 g total during the week prior to each dosing.
- Participants who use the following therapies prior to screening and are on a stable regimen should continue their use:
  - Oral contraceptives, hormone-replacement therapy, or other maintenance therapy.
- Participants who are taking non-biologic SOC therapy for UC during the study will remain on their SOC therapy. Specific instructions for each SOC is provided below:
  - Stable therapy for at least 2 weeks prior to screening with:
    - oral 5-ASA, or
    - oral glucocorticoid (not to exceed 20 mg/day prednisone equivalent at start of trial, may be weaned after dosing with study drug has been initiated).
  - Stable therapy for at least 8 weeks with:
    - azathioprine, or
    - 6-mercaptopurine (MP), or
    - methotrexate (and folic acid)
- *In the event of a systemic injection-related reaction (IRR) or systemic hypersensitivity AE: participants may receive pre-medication with paracetamol and antihistamines (as per local guidelines) prior to the next administration of study drug.*

### **Prohibited Therapy**

As a general rule, no concomitant medication will be permitted, with the exception of medications to treat AEs and those specified as permitted therapies, unless the rationale for exception is discussed and clearly documented between the Investigator and the Sponsor.

Use of the following therapies will be prohibited during the study and for at least 14 days or at least 5 half-lives prior to initiation of study treatment, whichever is longer unless otherwise specified below:

[figure not shown]
- Any rectal therapy
- Doses of glucocorticoids exceeding 20 mg/day of prednisone or equivalent
- Non-steroidal anti-inflammatory medications (e.g.: ibuprofen, naproxen) due to a propensity for these treatments to worsen inflammation in ulcerative colitis.

Calcineurin inhibitors (e.g., tacrolimus, cyclosporine) and any immune system targeted biological therapy within 12 weeks or 5 half-lives, whichever is longer, before the start of screening.

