### **Length of Study**

The total duration of the study for each participant will be approximately 19 weeks, divided as follows:

- Screening: Up to 5 weeks (35 days).
- Dosing Period: Day 1 to Day 43.
- In-clinic period: From Day –1 to Day 2 for the first dose, from Day 15 to Day 16 for the second dose, from Day 29 to Day 30 for the third dose, and from Day 43 to Day 44 for the last dose.
- Final follow-up: Day 99 ± 3 days (8 weeks post last dose).

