**Table 1 Schedule of Activities – Main Table (cont.)**

- a) A 35-day maximum screening period will begin with the first assessment, not from consent.
- b) Participants can be consented up to 3 months prior to randomization.
- c) Randomization may be conducted on Day -1 or Day 1 prior to first dose.
- d) A complete physical examination will be performed at screening (including height and weight), and abbreviated physical examinations at all other visits (no height measurement needed; weight only).
- e) Single measurements of vital signs to be taken before blood collection for laboratory tests but after ECG collection when scheduled at the same time point. Includes single measurements of systolic and diastolic blood pressure, pulse rate, body temperature (tympanic) and respiratory rate. All measurements to be taken after the participant has rested in a supine position for at least 5 minutes. *Vital sign assessments post-dose can be done with a deviation of ± 15 minutes.*
- f) QuantiFERON-TB Gold testing should be performed.
- g) Clinical genotyping is mandatory in countries where permitted.
- h) ECGs should be performed prior to any scheduled vital sign measurements and blood draws. 12-lead ECGs will be obtained in triplicate (three consecutive interpretable 12-lead ECGs within a 2 - 5 minute interval) after the participant has been in a supine position for at least 10 minutes. Automated ECG intervals (PR [PQ], QRS, QT, QTcF) and HR will be captured or calculated, and the changes in T-wave and U-wave morphology will be documented. Measure baseline prior to endoscopy if endoscopy performed on the same day. *ECG assessments post-dose can be done with a deviation of ± 15 minutes.*
- i) Safety tests can be repeated during screening period at discretion of Investigator.
- j) Hepatitis B and HIV 1/2 antibody testing; HCV PCR.
- k) Serum beta-human chorionic gonadotropin (β-HCG) at screening, urine on all other occasions (women of childbearing potential only).
- l) Drugs of abuse screen to include at minimum: amphetamines, barbiturates, cocaine, opiates, and benzodiazepines. Additional testing optional to local standards.
- m) Endoscopy to be performed in the morning prior to dose on Day 29.
- n) *Clostridium difficile* ELISA.

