### **Prior/Concomitant Therapy**

18. Use of calcineurin inhibitors (e.g., tacrolimus, cyclosporine), vedolizumab, anti-TNF $\alpha$  therapeutic or any other immune system–targeted biological therapy within 12 weeks or 5 half-lives, whichever is longer, prior to screening.
19. Rectal therapy with 5-ASA or corticosteroids within 2 weeks of screening.
20. Use of any investigational drug within 12 weeks of screening.
21. Leukocyte apheresis within 12 weeks of screening.
22. Live vaccine(s) within one month prior to screening, or plans to receive live vaccines during the study or within 28 days of the last dose.

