### **5.4 SCREEN FAILURES**

Screen failures are defined as participants who consent to participate in the clinical study but are not subsequently randomized to study treatment/entered in the study.

The Investigator will maintain a screening log to record details of all participants screened and to confirm eligibility or record reasons for screening failure.

Individuals who do not meet the criteria for participation in this study (screen failure) may be re-screened. Re-screened participants should be assigned the same participant number as for the initial screening.

For re-screened participants, the following specific criteria must be met:

- Screening colonoscopy or flexible sigmoidoscopy for inclusion must be completed within 3 weeks prior to first dose.
- Serologies for hepatitis B, HIV, and PCR for HCV need not be repeated, and screening for latent tuberculosis infection need not be repeated if already done.
- Women of child bearing potential must repeat pregnancy testing.

- Screening laboratory evaluation beyond those itemized above must be completed within 35 days of the starting dose.
- For participants who were initially excluded due to active *Clostridium difficile*-related infection, participants must have completed therapy and have been stable off therapy for at least 7 days prior to repeat *Clostridium difficile* testing for Test of Cure (TOC). Those who test negative may be eligible for re-enrollment.

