### **6.5.2 Prohibited Therapy**

All medications (prescription and OTC) taken within 30 days of study screening will be recorded on the appropriate eCRF.

As a general rule, no concomitant medication will be permitted, with the exception of medications to treat AEs and those specified (Section 6.5.1), unless the rationale for exception is discussed and clearly documented between the Investigator and the Sponsor.

Use of the following therapies will be prohibited during the study and for at least 14 days or at least 5 half-lives prior to initiation of study treatment, whichever is longer unless otherwise specified below:

- Unless covered by the exceptions described in Section 6.5.1:
  - Any rectal therapy.
  - Doses of glucocorticoids exceeding 20 mg/day of prednisone or equivalent
  - Non-steroidal anti-inflammatory medications (e.g., ibuprofen, naproxen) due to a propensity for these treatments to worsen inflammation in ulcerative colitis.
- Calcineurin inhibitors (e.g., tacrolimus, cyclosporine) and any other immune system targeted biological therapy 12 weeks or 5 half-lives, whichever is longer, before the start of screening.

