## **8.1 EFFICACY ASSESSMENTS**

Flexible sigmoidoscopy (or colonoscopy at screening if required by inclusion criteria) will be performed at the time-points specified in the SoA (see Section 1.3). The endoscopy will be centrally read and scored using the MCS-ES and UCEIS scoring systems. The Endoscopy subscore of the Mayo Score will be modified so that a value of 1 does not include friability. Sedation and preparation for colonoscopy or flexible sigmoidoscopy may follow local standards.

Mucosal biopsies will be obtained during flexible sigmoidoscopy at the most affected area 10 to 20 cm from the anal verge at screening/baseline and at Day 29 (Week 4) and Day 57 (Week 8) assessments. Biopsies will be assessed by standard histology for changes in inflammatory activity as measured by the Geboes Score ([Geboes et al. 2000](#)), Robarts Histology Index ([Mosli et al. 2017](#)) and the Nancy Histology Index ([Marchal-Bressenot et al. 2017](#)).

Additional details will be provided in the Procedural Manual.

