## **8.10          TIMING OF STUDY ASSESSMENTS**

### **8.10.1       Screening and Pre-treatment Assessments**

Written informed consent for participation in the study must be obtained before performing any study-specific screening tests or evaluations. Informed consent may be obtained up to 3 months prior to randomization. Screening start will be defined as the first assessment done after signature of the informed consent form. Informed Consent Forms (ICFs) for enrolled participant and for participants who are not subsequently enrolled will be maintained at the study site.

All screening and pre-treatment assessments must be completed and reviewed to confirm that participants meet all eligibility criteria. The Investigator will maintain a screening log to record details of all participants screened and to confirm eligibility or record reasons for screening failure.

An Eligibility Screening Form (ESF) documenting the Investigator's assessment of each screened participant with regard to the protocol's inclusion and exclusion criteria is to be completed by the Investigator and kept at the investigational site.

Screening and pre-treatment assessments will be performed within 35 days prior to Day 1 unless otherwise specified.

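### The NSAID wash-out is counted back from first dose, so no minimum NSAID-free interval is guaranteed before the endoscopy and biopsies that set eligibility and baseline

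*Combined protocol and SAP*

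**What the plan says.** **The rule and its reason.** Section 6.5.2 makes NSAIDs "prohibited during the study and for at least 14 days or at least 5 half-lives prior to initiation of study treatment", taking the longer of the two periods. The synopsis has the same rule and gives the reason: "Non-steroidal anti-inflammatory medications (e.g.: ibuprofen, naproxen) due to a propensity for these treatments to worsen inflammation in ulcerative colitis".

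**When screening starts.** Footnote a of the Schedule of Activities reads "A 35-day maximum screening period will begin with the first assessment, not from consent". Section 8.10.1 agrees: "Screening start will be defined as the first assessment done after signature of the informed consent form".

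**The baseline measurement.** Table 1 places the pre-dose endoscopy and colon biopsies in the column running from D-36 to D-2, with no narrower timing. Section 8.1 has the biopsies taken "from the anal verge at screening/baseline and at Day 29 (Week 4) and Day 57 (Week 8) assessments". Inclusion criterion 5 requires an endoscopy subscore (MCS-ES) of at least 2 at screening. Section 9.3.4 analyses change from that baseline in MCS-ES, UCEIS, histology scores and the full Mayo score.

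**The one timing limit on the screening endoscopy.** For re-screened participants, section 5.4 says "Screening colonoscopy or flexible sigmoidoscopy for inclusion must be completed within 3 weeks prior to first dose". That limits how early the endoscopy may be. It sets no interval after an NSAID.

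**Other treatments are tied to screening.** Exclusion criterion 19 reads "Rectal therapy with 5-ASA or corticosteroids within 2 weeks of screening". Oral 5-ASA and glucocorticoids must have been stable for 2 weeks before screening (section 6.5.1). Calcineurin inhibitors and biologics have a look-back of 12 weeks or 5 half-lives from the start of screening (section 6.5.2). No exclusion criterion names NSAIDs. The 30-day medication history in sections 6.5.1 and 6.5.2 records use but does not restrict it.

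**The concern.** The ban exists because NSAIDs can aggravate the mucosal inflammation that endoscopy and histology score. The wash-out protects the day of first dose, whereas the measurement it should protect is made up to five weeks earlier and, in the schedule, is not repeated before dosing. A participant could therefore qualify on, or be given a baseline that includes, activity driven by a recent NSAID. If that activity settles once the NSAID is withdrawn, the improvement is counted in within-arm change and in response.

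What is at stake is the reading of secondary, preliminary efficacy. The partial Mayo score is collected again on Day 1, so the gap concerns endoscopy, histology and the endoscopic part of the full Mayo score.

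**Working it through.** **1. Does the in-study ban cover screening?** The synopsis says "The total duration of the study for each participant will be approximately 19 weeks". Screening of up to 35 days plus follow-up to Day 99 gives 35 + 99 = 134 days, and 134 / 7 = 19.1 weeks. The plan's figure is reproduced only with screening included, so the check uses this stricter reading: no NSAID from the first screening assessment onward.

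**2. Latest permitted NSAID use.** Let the endoscopy fall on D-x, k days after the first screening assessment. There is no Day 0.
- Wash-out limb, 14 days: D-14 to D-1 must be free, so last use is D-15 or earlier.
- In-study limb: last use is before D-(x+k), so D-(x+k+1) or earlier.

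**3. Guaranteed full NSAID-free days between last use and endoscopy.**

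max(x + k + 1, 15) - x - 1 = max(k, 14 - x)

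| Case | Guaranteed full days |
|---|---|
| k = 0, D-36 to D-14 | 0 |
| k = 0, D-13 | 1 |
| k = 0, D-2 | 12 |
| k = 3, minimum over all days | 3 |
| k = 7, minimum over all days | 7 |
| k = 10, minimum over all days | 10 |
| k = 14 or more | at least 14 |

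Because x is at least 2, the term 14 - x never exceeds 12. The full 14 days is guaranteed only when endoscopy comes at least 14 days after the first screening assessment. Measured as elapsed time from last use to endoscopy, each figure is one day larger.

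With k = 0, the zero applies on 36 - 14 + 1 = 23 of the 35 days from D-36 to D-2. If the window is taken to open at D-35 (section 8.10.1), it is 22 of 34. For re-screened participants with k = 0, it applies on D-21 to D-14, which is 8 days. These are counts of permitted days, not probabilities.

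**4. The other readings.** If screening were not part of the study, an NSAID could continue to D-15 and an earlier endoscopy could be done on it, so the gap would be wider. The 5-half-life limb exceeds 14 days only for half-lives above 14 × 24 / 5 = 67.2 hours, and it too counts from first dose.

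**5. Effect on scores.** The documents give neither the rate of NSAID use nor the effect of withdrawal, so no estimate is possible. For scale only, assume that m of the 8 active participants in a cohort improve by 1 MCS-ES point through withdrawal alone. The arm's mean change then shifts by m/8: 0 for m = 0, 0.125 for m = 1, 0.25 for m = 2.

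**The case against.** **Zero wash-out needs two things at once:** NSAID use up to the day before screening, and endoscopy as the first assessment. Appendix 8 (Version 4 rationale) says the screening window was lengthened partly so that endoscopy could be planned around a stool examination with a slow turnaround. Endoscopy will therefore often come later. This stands: zero is a permitted minimum. A reader might infer that baseline endoscopies were typically done with no wash-out, and the documents do not support that.

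**No bias between arms.** A reader might infer that the active-placebo comparison is biased. It is not, in expectation: assignment is randomised and blinded, and the rule is the same in both arms. Chance imbalance remains possible with about 2 placebo participants per cohort.

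**Cross-dose comparisons.** Dose levels are opened in sequence, so a reader might infer that comparisons between them are distorted. The same rule applies at every level, each cohort has its own placebo participants, and nothing in the documents suggests that NSAID use differs by dose. This inference is not supported.

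**Response.** A reader might take a 1-point MCS-ES fall as a response by itself. As section 9.3.4 is worded, endoscopic response also needs a UCEIS fall of at least 3 points.

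**Weight.** There is no formal hypothesis (section 9.1), efficacy is preliminary, and section 9.3.1 already summarises concomitant medications at baseline. All true, and it limits the importance of the point. But that summary does not relate NSAID use to the date of the baseline endoscopy.

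**Changing entry conditions mid-study** would affect mainly 15 mg participants. This is a fair criticism of re-anchoring on its own, and the reason it should only accompany the flag.

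**Conclusion.** The point holds as a cheap improvement. The wash-out is tied to first dose, although its stated purpose concerns inflammation that is scored at screening, and no other provision in the documents guarantees an NSAID-free interval before that endoscopy. The guaranteed minimum is max(k, 14 - x) full days. It is 0 when endoscopy is the first screening assessment on or before D-14, and larger when other assessments come first.

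This rests on three assumptions: screening counts as part of the study, the 14-day limb governs, and no unseen manual orders the assessments (section 8.1 leaves further detail to a Procedural Manual). That NSAID-driven activity would recede on withdrawal is plausible from the plan's own reason for the ban, but the documents do not quantify it.

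The consequence is confined to eligibility and to within-arm endoscopic and histologic change and response, with the endoscopic part of the full Mayo score. Its size is unknown. The primary safety objective is unaffected.

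**What to change.** **1. Main remedy, all dose levels.** From the medications already recorded from 30 days before screening (section 6.5.1), flag each participant with NSAID use within 14 days or 5 half-lives, whichever is longer, before the baseline endoscopy. Repeat the descriptive efficacy summaries without them. The record covers the 14-day period, and 5 half-lives for half-lives up to 30 / 5 = 6 days. The cost is one derived flag and a repeat of existing tables. With about 8 active and 2 placebo participants per cohort, the repeated summaries will rest on small numbers and should be read as a check.

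**2. Together with (1), for participants still to be enrolled.** State in sections 6.5.2 and 8.1 and in the Schedule of Activities that the screening endoscopy and biopsies are done only once the existing NSAID wash-out is complete. The length need not change. The window can hold a 14-day wait: last use on D-37 leaves D-36 to D-23 free (14 days) and endoscopy possible from D-22 to D-2 (21 days).

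The costs of (2) are about two weeks' wait for NSAID users and a small difference in entry conditions for later, mainly 15 mg, participants. The flag in (1) lets the sponsor check that difference. The reach of (2) is limited: if Cohorts 1 to 4 (section 2.3) each enrolled at least 10, an assumption drawn from the Version 5 rationale, at most 65 - 4 × 10 = 25 participants remain.

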## 1.2 SCHEMATIC OF STUDY DESIGN

An overview of the study design is provided in [Figure 1](#).

**Figure 1 Overview of Study Design**

The doses for dose level 1 (3.5 mg) and dose level 2 (7.5 mg) are based on results from the entry-in-human (EIH) Study WP39826, which supported safety, pharmacokinetics, and pharmacodynamics in healthy volunteers in single dosing. *Dose level 3 (15 mg) is based on initial analyses of results from repeat dosing with 3.5 and 7.5 mg in participants with ulcerative colitis in this study.*

## 1.3 SCHEDULE OF ACTIVITIES

The schedule of activities is provided in [Table 1](#) and [Table 2](#).

**Table 1 Schedule of Activities – Main Table**

Activity	Screening / Baseline a		Dose 1			Dose 1 Outpatient Visits				Dose 2		Outpatient Phone Call	Outpatient visit	Dose 3		Outpatient Phone Call	Outpatient visit
	D-36 to D-2	D-1	Day 1	Day 2	Day 4	Day 6	Day 8	Day 10	Day 15	Day 16	Day 19	Day 22	Day 29	Day 30	Day 33	Day 36	
Overall Study Day																	
Dose/Day		Dose 1/Day -1	Dose 1/Day 1	Dose 1/Day 2	Dose 1/Day 4	Dose 1/Day 6	Dose 1/Day 8	Dose 1/Day 10	Dose 2/Day 1	Dose 2/Day 2	Dose 2/Day 5	Dose 2/Day 8	Dose 3/Day 1	Dose 3/Day 2	Dose 3/Day 5	Dose 3/Day 8	
Time Relative (h)	***	***	0	24	72	120	168	216	336	360	432	504	672	696	768	840	
Visit Window						(+/-1)	(+/-1)				(+/-1)	(+/-1)	(+/-1)	(+/-1)	(+/-1)	(+/-1)	
Assessments																	
Informed Consent b	X																
Demography	X																
Medical History	X																
Randomization c	X																
Physical Examination d	X	X	X	X						X				X			
Vital Signs e	X	X	2	X						X	X			X	X		
Eligibility	X	X															
Tuberculosis Screening Test f	X																
Clinical Genotyping g		X															
ECG-12 lead h	X		2	X						X				X			
Hematology i	X	X		X			X		X				X	X		X	
Blood Chemistry i	X	X		X			X		X				X	X		X	
Urinalysis i	X	X		X			X		X				X	X		X	
Serology and viral PCR j	X																
Pregnancy Testing k	X	X								X				X			
Coagulation	X																
Alcohol breath or blood test	X	X															
Drugs of abuse l	X	X															
Colonoscopy or flexible sigmoidoscopy m	X													X			
Colon Biopsy	X													X			
Stool Clostridium difficile n	X																
Stool Ova and Parasites	X																
In-house period		X	X	X						X	X			X	X		
Drug/Placebo Administration			X							X				X			
Standard meal o		X	X	X						X	X			X	X		
PK sampling p			3	X	X	X	X	X	X	2			X	X		X	
Blood flow cytometry		X	X	X			X	X	X	X			X	X		X	
Blood epigenetic testing			X			X	X	X	X	X							
Soluble PD biomarkers q			X	X	X	X	X	X		X				X			
Soluble disease biomarkers n			X	X						X				X			
sCD25 w		X	X			X	X	X		X				X			
Fecal Calprotectin v			X							X							
Abdominal skinfold thickness			X														
Anti-drug antibodies			X						X	X			X	X			
Local pain/Skin reactivity assessments x			X						X				X				
Clinical Outcome Assessment y	X		X				X		X				X	X		X	
Safety Phone Call z												X				X	
Safety biomarkers u																	
Adverse Events									X								
Previous and Concomitant Treatments									X								

**Table 1 Schedule of Activities – Main Table (cont.)**

Activity	Dose 4		Dose 4 Outpatient Visits						Follow Up visit	Outpatient visit	Hypersensitivity/ IRR (≥ Grade 2)	Early Termination Visit
	Day 43	Day 44	Day 46	Day 48	Day 50	Day 52	Day 57	Day 71				
Overall Study Day									Day 99 w	Unscheduled visit	Unscheduled visit	Unscheduled visit
Dose/Day	Dose 4/Day 1	Dose 4/Day 2	Dose 4/Day 4	Dose 4/Day 6	Dose 4/Day 8	Dose 4/Day 10	Dose 4/Day 15	Dose 4/Day 29				Unscheduled visit
Time Relative (h)	1008	1032	1080	1128	1176	1224	1344	1680	2376	Anytime	Anytime	Anytime
Visit Window				(+/- 1)	(+/- 1)	(+/- 1)	(+/- 1)	(+/- 1)	(+/- 3)			
Assessments												
Informed Consent b												
Demography												
Medical History												
Randomization c												
Physical Examination d	x									x	x	x
Vital Signs e	2	x								x	x	x
Eligibility												
Tuberculosis Screening Test f												
Clinical Genotyping g												
ECG-12 lead h	2	x								x	x	x
Hematology i	x				x x		x	x	x	x	x	x
Blood Chemistry i	x				x x		x	x	x	x	x	x
Urinalysis i	x				x x		x	x	x	x	x	x
Serology and viral PCR j												
Pregnancy Testing k	x									x	x	x
Coagulation										x	x	x
Alcohol breath or blood test											x	
Drugs of abuse l											x	
Colonoscopy or flexible sigmoidoscopy m								x				
Colon Biopsy								x				
Stool Clostridium difficile n												
Stool Ova and Parasites												
In-house period	x	x										
Drug/Placebo Administration	x											
Standard meal o	x	x										
PK sampling y	3	x	x	x	x	x	x	x	x	x	x	x
Blood flow cytometry	x				x	x	x	x	x			x
Blood epigenetic testing	x				x	x	x	x	x			x
Soluble PD biomarkers p	x	x	x	x				x				x
Soluble disease biomarkers q	x	x						x		x	x	
sCD25 w	x	x			x	x			x	x	x	
Fecal Calprotectin r	x				x x							
Abdominal skinfold thickness												
Anti-drug antibodies	x							x	x	x	x	x
Local pain/Skin reactivity assessments r	x								x	x	x	x
Clinical Outcome Assessment s	x				x		x	x	x	x	x	x
Safety Phone Call												
Safety biomarkers u								x			x	
Adverse Events								x				
Previous and Concomitant Treatments								x				

